### 7.2.3 Expectedness

Adverse events can be expected or unexpected.

#### 7.2.3.1 Expected Adverse Event

Expected adverse events are those that have been previously identified as resulting from administration of the agent. For the purposes of this study, an adverse event is considered expected when it appears in the current adverse event list, the Investigator's Brochure, the package insert or is included in the informed consent document as an associated risk. Refer to Section 6.1 for a listing of expected adverse events associated with the study agent(s).

---

CONFIDENTIAL

This document is confidential. Do not disclose or use except as authorized.

### 7.2.3.2 Unexpected Adverse Event

For the purposes of this study, an adverse event is considered unexpected when it varies in nature, intensity or frequency from information provided in the current adverse event list, the Investigator's Brochure, the package insert or when it is not included in the informed consent document as an associated risk.

### 7.2.4 Attribution

Attribution is the relationship between an adverse event or serious adverse event and the study treatment. Attribution will be assigned as follows:

- Definite – The AE is clearly related to the study treatment.
- Probable – The AE is likely related to the study treatment
- Possible – The AE may be related to the study treatment.
- Unlikely - The AE is doubtfully related to the study treatment.
- Unrelated - The AE is clearly NOT related to the study treatment

## 7.3 Adverse Event Characteristics

The descriptions and grading scales found in the revised NCI Common Terminology Criteria for Adverse Events (CTCAE) version 4.0 will be utilized for AE reporting. All appropriate treatment areas should have access to a copy of the CTCAE version 4.0. A copy of the CTCAE version 4.0 can be downloaded from the CTEP web site  
[http://ctep.cancer.gov/protocolDevelopment/electronic\\_applications/ctc.htm](http://ctep.cancer.gov/protocolDevelopment/electronic_applications/ctc.htm).

AEs that are listed above should be reported only if the adverse event varies in nature, intensity or frequency from the expected toxicity information which is provided.

## 7.4 Expedited Adverse Event Reporting

All serious adverse event (SAE) that occur after the initial dose of study treatment, during treatment, or within 30 days of the last dose of ivosidenib must be reported to the Coordinating Center and the Principal Investigator, [name]., on the local institutional SAE form.

This includes events meeting the criteria outlined in Section 7.2.2, as well as the following:

- Grade 2 (moderate) and Grade 3 (severe) events that are unexpected and at least possibly related/associated with the intervention.
- All Grade 4 (life-threatening or disabling) events that are unexpected or not specifically listed in the protocol as not requiring reporting.
- All Grade 5 (fatal) events while the participant is enrolled and actively participating in the trial OR when the event occurs within 30 days of the last study intervention. Note: If the participant is in long term follow up, report the death at the time of continuing review.

For multi-center studies where a DF/HCC investigator is serving as the Overall Principal Investigator, each participating institution **must** abide by the reporting requirements set by the

---

CONFIDENTIAL

This document is confidential. Do not disclose or use except as authorized.

DF/HCC.

In the event of an unanticipated problem or life-threatening complications, treating investigators must immediately notify the overall PI.

#### 7.4.1 DF/HCC Expedited Reporting Guidelines

Investigative sites within DF/HCC will report AEs directly to the DFCI Office for Human Research Studies (OHRS) per the DFCI IRB reporting policy.

Other investigative sites will report AEs to their respective IRB according to the local IRB's policies and procedures in reporting adverse events. A copy of the submitted institutional AE form should be forwarded to the Coordinating Center within the timeframes detailed in the table below. The Coordinating Center will submit AE reports from outside institutions to the DFCI OHRS according to DFCI IRB policies and procedures in reporting adverse events.

Attribution	DF/HCC Reportable AEs				
	Gr. 2 & 3 AE Expected	Gr. 2 & 3 AE Unexpected	Gr. 4 AE Expected	Gr. 4 AE Unexpected	Gr. 5 AE Expected or Unexpected
Unrelated Unlikely	Not required	Not required	5 calendar days #	5 calendar days	24 hours*
Possible Probable Definite	Not required	5 calendar days	5 calendar days #	5 calendar days	24 hours*
# If listed in protocol as expected and not requiring expedited reporting, event does not need to be reported.					
* For participants enrolled and actively participating in the study or for AEs occurring within 30 days of the last intervention, the AE should be reported within 1 business day of learning of the event.					

Participating investigators must report each adverse event to the Coordinating Center in accordance with these timeframes. In the event that the participating investigator does not become aware of the adverse event immediately (e.g., participant sought treatment elsewhere) or within the reporting timeframes listed in the table above, the participating investigator is to report the event within 1 business day after learning of it and document the time of his or her first awareness of the adverse event.

### 7.5 Expedited Reporting to the Food and Drug Administration (FDA)

The Overall PI, as study sponsor, will be responsible for all communications with the FDA. The Overall PI will report to the FDA, regardless of the site of occurrence, any serious adverse event that meets the FDA's criteria for expedited reporting following the reporting requirements and timelines set by the FDA.

### 7.6 Expedited Reporting to Hospital Risk Management

Participating investigators will report to their local Risk Management office any participant

---

CONFIDENTIAL

This document is confidential. Do not disclose or use except as authorized.

safety reports or sentinel events that require reporting according to institutional policy.

## **7.7 Safety Reporting to Servier**

A listing of all SAEs should be reported to Servier on a quarterly basis. Any adverse event requiring expedited reporting (serious, unexpected event suspected of being related to AG-120) will be reported by the Coordinating Center to Servier immediately but no later than 24 hours after regulatory submission .

Should the site become aware of a pregnancy or drug mis-dose/overdose, this should be reported to the Coordinating Center and Overall PI within 24 hours of becoming aware.

The Coordinating Center will submit reports to Servier to: [[contact]](mailto:[contact])

## **7.8 Routine Adverse Event Reporting**

All Adverse Events must be reported in routine study data submissions to the Overall PI on the toxicity case report forms. AEs reported through expedited processes (e.g., reported to the IRB, FDA, etc.) must also be reported in routine study data submissions. All adverse events that occur through 30 days after the last dose of study drug will be recorded in the protocol-specific case report forms.

# **8. PHARMACEUTICAL INFORMATION**

A list of the adverse events and potential risks associated with ivosidenib can be found in Section 7.1.

## **8.1 Ivosidenib**

### **8.1.1 Description**

Ivosidenib is also known as AG-120 or AGI-16678.

AG-120 demonstrated good oral bioavailability, rapid absorption, and a long  $t_{1/2}$  in subjects with IDH1m AML and solid tumors, supporting a QD dosing regimen. Following multiple doses of AG-120, steady state was reached within 15 days, with approximately 2-fold accumulation in plasma exposure. Plasma exposure of AG-120 increased less than dose proportionally from 100 to 1200 mg. Results from Studies AG120-C-001 and AG120-C-002 indicate that plasma 2-HG levels were substantially reduced in subjects with an IDH1 mutation (achieving levels similar to those in healthy volunteers) at dose ranging from 200 to 1200 mg QD. Multiple doses of AG-120 also decreased 2-HG levels in bone marrow (AML) and tumor biopsies (cholangiocarcinoma, chondrosarcoma) at dose ranging from 200 mg to 1200 mg QD. Maximal inhibition of 2-HG in plasma did not appear to change upon multiple daily dosing with AG-120.

---

CONFIDENTIAL

This document is confidential. Do not disclose or use except as authorized.

#### 8.1.2 Form

Ivosidenib/ AG-120 tablets are available in 250 mg strength for clinical studies.

AG-120 250 mg film-coated tablets are blue oval shape tablets containing 250 mg of AG-120.

AG-120 250 mg tablets contain the inactive ingredients hypromellose acetate succinate, microcrystalline cellulose, croscarmellose sodium, sodium lauryl sulfate, colloidal silicon dioxide, and magnesium stearate. AG-120 250 mg film-coated tablets also include the inactive ingredient Opadry® II Blue.

#### 8.1.3 Packaging

Ivosidenib/AG-120 tablets are supplied in appropriate containers and are labeled appropriately as investigational product for clinical studies. Tablets will be supplied in high density polyethylene (HDPE) bottles with a desiccant silica gel and child-resistant closures with heat induction seal.

#### 8.1.4 Availability

Ivosidenib/AG-120 will be provided by Servier Pharmaceuticals, Inc.

#### 8.1.5 Administration

Drug will be administered orally, once per day, at doses as specified above in the Treatment Plan (section 5).

Subjects may take ivosidenib/AG-120 tablets with or without food. To minimize the effects of a high-fat meal on AG-120 exposure, subjects should avoid consuming a high-fat meal when AG-120 is administered with food. All subjects will also be advised to avoid grapefruit and grapefruit products.

#### 8.1.6 Accountability

The investigator, or a responsible party designated by the investigator, should maintain a careful record of the inventory and disposition of the agent using the NCI Drug Accountability Record Form (DARF) or another comparable drug accountability form.

### **9. BIOMARKER, CORRELATIVE, AND SPECIAL STUDIES**

Correlative studies for 2-Hydroxyglutarate and minimal residual disease will be performed on all participants' samples. Next generation and whole genome sequencing will be performed only on samples from DF/HCC participants.

---

CONFIDENTIAL

This document is confidential. Do not disclose or use except as authorized.

## **9.1 2-Hydroxyglutarate analysis**

We will measure plasma and marrow levels of 2-hydroxyglutarate.

- Pretreatment: Blood 2 mL , Bone marrow aspirate 2 mL
- Day 8 (Range Days 6-10): Blood 2 mL
- Day 15 (Range Days 13-16): Blood 2 mL
- Day 30: Blood 2 mL
- Day 60: Blood 2 mL
- At any point of relapse: Blood 2 mL, Bone marrow aspirate 2 mL (if available)

Blood will be collected in 2mL lavender top K2EDTA tubes. Collected samples will be stored on ice until centrifuged. Plasma will be stored frozen at -80°C (+/- 10°C) until shipped.

Bone marrow will be collected in 4mL Na Heparin tubes and then aliquoted into cryovials that will be stored frozen at -80°C (+/- 10°C) until shipped.

Frozen samples will be shipped on dry ice (shipping out on Monday, Tuesday, or Wednesday) to

## **9.2 Next-generation and whole genome sequencing (DF/HCC participating sites ONLY)**

The following volumes of blood and aspirated bone marrow will be required:

- Pretreatment: Blood 15 mL x 2, Bone marrow aspirate 15 mL
- Day 8 (Range Days 6-10): Blood 15 mL
- Day 15 (Range days 13-16): Blood 15 mL
- Day 30: Blood 15 mL
- Day 60: Blood 15 mL,
- At any point of relapse: Blood 15 mL, Bone marrow aspirate 15 mL (if available)

Bone marrow aspirate and peripheral blood shall be collected in purple-top (EDTA) tubes.

All specimens should be maintained at room temperature and delivered within one day to the processing laboratory. Specimens may be shipped via FedEx priority overnight Monday through Thursday (excluding holidays). For after-hours / evening collections, specimens may be maintained at room temperature and shipped within 4 days of collection.

Samples will be sent to:

CONFIDENTIAL

This document is confidential. Do not disclose or use except as authorized.

MGH Tissue Repository  
c/o [name]  
[name]  
[name]  
[contact]

All samples will be processed in a CLIA certified lab. DNA obtained from blood and bone marrow may be subjected to broader sequence analysis (whole exome or genome).

Whole genome sequencing (WGS) will allow us to look at the clonal architecture of *IDH1*-mutant disease at various time points during maintenance after hematopoietic stem cell transplant. This will help us look at which clones or subclones respond to therapy and whether the disease course is influenced by the outgrowth of *IDH*-wildtype clones.

We will also perform next-generation sequencing (NGS) to assess for mutational burden (i.e. the fraction of AML cells harboring *IDH* mutations, corrected for copy number) at various time points. We will utilize the SNaPshot genotyping analysis platform to perform these analyses. This assay uses multiplex polymerase chain reaction technology for single nucleotide variant and insertion/deletion detection in genomic DNA. The sequencing targets hotspots and exons including *IDH1/2*. We will monitor the dynamics of *IDH1* mutational burden and assess for the presence / absence of the *IDH* mutant allele at these timepoints.

### **9.3 Minimal Residual Disease (MRD)**

We will measure MRD from bone marrow aspirate whenever possible. If bone marrow aspirate is not available, peripheral blood should be collected.

- Pretreatment: Bone marrow aspirate 8 mL (or peripheral blood)
- Pre-Cycle 12: Bone marrow aspirate 8 mL (or peripheral blood)
- At any point of relapse or discontinuation from study: Bone marrow aspirate 8 mL (or peripheral blood)

Sample will be collected in 8 mL CPT Sodium Heparin tubes. Collected samples can be stored at room temperature until processed. **Samples must be processed within 4 hours of collection.** Processed cells will be aliquoted into cryovials that will be stored frozen at -80°C (+/- 10°C) until they are shipped.

Detailed collection, processing and shipping instructions are provided in a separate laboratory manual.

Frozen samples will be batch shipped to:

Sysmex Inostics GmbH  
ATTN: [name]  
[name]  
[name]

---

CONFIDENTIAL

This document is confidential. Do not disclose or use except as authorized.

[name]  
 Germany

All specimens should be labeled with study ID (#18-123), participant study ID number, visit cycle/day, date and time of collection, specimen type, and must be accompanied by the appropriate requisition form and inventory manifest.

On the day of shipping, the Coordinating Center should be emailed a copy of the inventory manifest, date of shipment and the tracking number.

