### 1.3 Secondary Objectives

To detect and categorize, according to severity, ivosidenib-related toxicities in patients with *IDH1*-mutant myeloid neoplasms receiving ivosidenib after hematopoietic stem cell transplantation.

To examine the cumulative incidence of acute GVHD from start of ivosidenib in patients with *IDH1*-mutant myeloid neoplasms who receive ivosidenib after hematopoietic stem cell transplantation.

To examine the cumulative incidence of chronic GVHD from start of ivosidenib in patients with *IDH1*-mutant myeloid neoplasms who receive ivosidenib after hematopoietic stem cell transplantation.

To monitor plasma and marrow 2-hydroxyglutarate levels in patients with *IDH1*-mutant myeloid neoplasms who receive ivosidenib after hematopoietic stem cell transplantation.

To assess *IDH* clonal evolution and mutational burden in patients with *IDH1*-mutant myeloid neoplasms who receive ivosidenib after hematopoietic stem cell transplantation.

To measure minimal residual disease (MRD) in patients with *IDH1*-mutant myeloid neoplasms who receive ivosidenib after hematopoietic stem cell transplantation, through measurement of mutant IDH1 (mIDH1) allelic burden.

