#### 2.5.4 Minimal Residual Disease (MRD)

In the phase 1 study of ivosidenib in myeloid malignancies, a proportion of relapsed and refractory patients were found to have cleared the mutant (mIDH1) allelic burden (Stone 2017). Indeed, MRD-negativity was observed in 7 of 25 (28%) R/R AML patients who achieved CR, and those with MRD-negative CR had improved CR duration and overall survival, albeit the dataset was small. MRD-negativity by mIDH1 status was also observed in 5 of 9 patients with untreated AML who achieved CR or CRh. We therefore seek to assess MRD clearance by measuring mIDH1 allelic burden at time points throughout the study.

---

CONFIDENTIAL

This document is confidential. Do not disclose or use except as authorized.

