## **5.8 Criteria for Taking a Participant Off Study**

Participants will be removed from study when any of the following criteria applies:

- Lost to follow-up
- Withdrawal of consent for data submission
- Death

The reason for taking a participant off study, and the date the participant was removed, must be documented in the case report form (CRF). The DF/HCC research team will update the relevant Off Treatment/Off Study information in the CTMS, OnCore in accordance with DF/HCC policy REGIST-101. The Coordinating Center will update this information for external site participants.

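### Read literally, Section 9.3 takes no post-baseline MRD sample from participants who stop ivosidenib before cycle 12 without relapse, and it lets blood stand in for marrow with no analysis by specimen

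*Combined protocol and SAP*

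**What the plan says.** Section 1.3 makes MRD a secondary objective, to be measured "through measurement of mutant IDH1 (mIDH1) allelic burden". The background in Section 2.5.4 goes a step further: "We therefore seek to assess MRD clearance by" following that burden over the study.

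Section 9.3 sets the sampling. On specimen it says "We will measure MRD from bone marrow aspirate whenever possible", and then "If bone marrow aspirate is not available, peripheral blood should be collected". After the pretreatment sample there is one scheduled on-treatment sample, "Pre-Cycle 12: Bone marrow aspirate 8 mL (or peripheral blood", and one off-schedule line: "At any point of relapse or discontinuation from study: Bone marrow aspirate 8 mL (or peripheral blood". Tubes must carry the specimen type on the label.

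Section 5.8 defines leaving the study: "Participants will be removed from study when any of the following criteria applies". It lists three criteria. The first is "Lost to follow-up"; the others are withdrawal of consent to submit data, and death. Stopping treatment is a separate status under Section 5.6. Sections 6.3.1, 6.3.2, 6.7.1 and 6.7.2 say that participants taken off drug for toxicity remain on study for survival and other outcomes.

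Section 11.4 gives summary statistics for allele burdens at each time point. Section 13 says that laboratory correlatives will be reported descriptively. Neither separates blood from marrow, defines clearance, or says how a missing follow-up sample is handled.

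**The concern.** There are two gaps, and both affect the same small data set.

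The first is the trigger. It is attached to leaving the study, but the participants whose follow-up sample would otherwise be missed are those who leave treatment. The protocol keeps these two events apart everywhere else. A site that follows the text exactly will not draw the sample. A site that reads it loosely will, so collection could also differ between centres.

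The second is the specimen. A participant may have marrow at baseline and blood later, or the reverse. Mutant IDH1 burden need not be equal in the two. A change of specimen could then pass for clearance or for reappearance of the mutation, and the planned summaries would not show it.

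At stake is the interpretation of a descriptive secondary result. The recommended phase 2 dose and the safety assessment are not affected.

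**Working it through.** The plan states no figure for MRD, so there is none to reproduce. Its one precision statement (Section 13, 16 participants, 90% interval within ±22%) concerns toxicity. The check is therefore a reading of the text, followed by illustrations.

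**Step 1: which participants reach an MRD time point after baseline?** Cycles are 28 days, so the pre-cycle 12 sample falls after 11 × 28 = 308 days.

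| Path | Post-baseline MRD sample under 9.3 |
|---|---|
| Still treated at cycle 12 | Pre-cycle 12, about day 308 |
| Relapses at any time | At relapse |
| Stops before cycle 12, no relapse, stays on study | None, unless relapse follows later |
| Lost, withdraws consent for data, or dies | Nominally due, but not realistically obtainable or usable |

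The gap is the third row: stopping for toxicity, GVHD or personal decision. Section 11 requires a disease assessment at the End of Treatment visit for those who stop for reasons other than progression, but it does not name MRD.

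**Step 2: can specimens be mixed within a participant?** Yes. Section 9.3 allows blood separately at each of its time points and has no same-specimen rule. By contrast, Sections 9.1 and 9.2 draw blood at every time point and add marrow at pretreatment and, if available, at relapse. Those two analyses always have a like-for-like blood series; MRD may not.

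**Step 3: what could missing samples do? (assumptions)** Take 16 participants at the recommended dose, all with detectable mutant IDH1 at baseline. Let k be unsampled and let half of the 16 − k sampled have cleared, so c = (16 − k)/2. The observed proportion is 50%. The true proportion for all 16 lies between c/16 (no unsampled participant cleared) and (c + k)/16 (all of them cleared).

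| k | Observed | Lower bound | Upper bound |
|---|---|---|---|
| 2 | 7/14 | 7/16 = 44% | 9/16 = 56% |
| 4 | 6/12 | 6/16 = 38% | 10/16 = 63% |
| 6 | 5/10 | 5/16 = 31% | 11/16 = 69% |

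If those who stop early clear at the same rate as those sampled, the bias is zero.

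**Step 4: what could switching do? (assumptions)** Suppose all 16 are marrow-positive at baseline and none truly clears. Let f be the share whose later sample is blood, and s the share of marrow-positives that blood detects. Apparent clearance is f × (1 − s).

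- f = 0.1, s = 0.9: 0.1 × 0.1 = 1%, or 0.16 of 16
- f = 0.3, s = 0.7: 0.3 × 0.3 = 9%, or 1.44 of 16
- f = 0.5, s = 0.5: 0.5 × 0.5 = 25%, or 4 of 16

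A switch from blood to marrow under the same assumptions would work the other way and could hide clearance.

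None of k, f or s is given in the documents. Section 5.2.1 requires no evidence of residual disease at treatment start, so the number with a detectable baseline may be well below 16.

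**The case against.** The strongest reply has several parts.

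- Blood is a fallback, not a free choice. The calendar schedules marrow at pretreatment, before cycle 12 and at relapse, so mixing should be the exception. Specimen type is labelled, so results could be separated. This stands, and it lowers the likely extent of mixing. It does not supply the missing analysis rule. Section 9.3 also defers detailed collection instructions to a laboratory manual that is not among the documents, so a matching rule there cannot be excluded.
- The trigger may simply be loose wording for end of treatment. That is plausible, but Sections 5.6, 5.8 and 6 distinguish the two, so the wording needs correcting.
- The empty calendar cells at End of Treatment prove little. The correlative-blood row names 2-HG, NGS and WGS, and it is equally empty before cycle 12, where Section 9.3 plainly requires MRD. This stands; the point rests on Sections 9.3 and 5.8, not on the calendar.
- At DF/HCC sites, Section 9.2 gives a parallel blood series to day 60 and at relapse. That is useful support, but it is planned at those sites only and is a separate analysis from the MRD measurement.
- The objective in Section 1.3 is to measure MRD. Clearance appears only in the background, and no MRD-negative proportion is planned. This stands, and it limits the weight of the point.

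A reader might also infer that the pre-cycle 12 group is selected to look favourable. That group does exclude earlier relapsers, but relapsers are sampled under their own trigger and are in the MRD data. Nothing in the documents shows that those who stop for toxicity or GVHD have worse MRD.

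**Conclusion.** The point holds as a risk of bias, not as demonstrated bias. Followed literally, the text takes no post-baseline MRD sample from participants who stop before cycle 12 without relapse, and it allows specimen mixing that the planned summaries would not reveal. It does not lose all early stoppers, because relapsers are sampled.

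Size and direction cannot be derived. The ranges above (for example 38% to 63% around an observed 50% with 4 of 16 unsampled, or 1% to 25% apparent clearance from switching) rest wholly on assumed stopping rates, blood detection rates and baseline positivity. A firm statement that the MRD results are biased, or biased upwards, would go beyond the documents. The change is still worth making: the objective is a stated secondary one, and samples not taken cannot be recovered at analysis.

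**What to change.** 1. In Section 9.3, keep the relapse trigger. Replace the trigger on leaving the study with the End of Treatment visit, if treatment stops before the pre-cycle 12 sample. Blood suffices, and blood is already drawn at that visit.
2. Add an MRD row to the Section 10 calendar at pretreatment, pre-cycle 12, relapse and End of Treatment.
3. In Section 11.4 or 13, state that within-participant change and clearance are reported only between samples of the same specimen type, and that clearance is reported among participants with detectable mutant IDH1 at baseline.
4. Report how many participants lack a follow-up MRD sample, and why.

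To make a like-for-like comparison possible when the later sample is blood, one blood tube at pretreatment may be added. Running MRD on the marrow already scheduled before cycle 6 is optional.

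The cost is one 8 mL tube per non-relapsing early stopper and, if adopted, one per participant at pretreatment (up to 22 evaluable participants, plus any who are replaced). Each tube needs processing within 4 hours at the site, and there are a few more assays in the existing batch shipments. No extra marrow procedure and no extra participants are needed.
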